	
As of Protocol Amendment 4.0, the recruitment will be stopped and the study population will be unblinded.
 
For patients randomized to the placebo group, no further protocol visits will be performed except for the concluding visit and no further doses will be administered. As it cannot be excluded that one or more patients may benefit from this treatment on an individual basis, patients receiving active treatment (patients not on placebo, and patients that have not already completed or interrupted their MAGE-A3 ASCI treatment) will be offered the option to continue the administration of the study treatment until the last dose is administered or until recurrence, whichever comes first, or until the patient or the investigator decides to stop the study treatment. Therefore, the study will continue only with patients from the active treatment group who will decide to stay in the study. Treatment will not be possible anymore after 30 November 2016.
 
During the treatment period, safety monitoring will continue as initially foreseen during the treatment period. In the best interest of the patient, additional biological samples for protocol research purposes (evaluation of the immune response, translational research) will not be taken nor collected.
 
The primary and secondary objectives will not be assessed as planned. All clinical data collected in the study will be analysed descriptively. By default, for each biological sample already collected in the scope of this study and not tested yet, testing will only be done if a scientific rationale remains relevant despite the premature termination of the study. In that case, testing will be in compliance with the protocol and ICF signed by the patient. The immune response will not be evaluated anymore as the immune response to IP administration was confirmed in other ASCI trials, but did not show any correlation with the potential efficacy.

--	--

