#### **4. DESIGN OF THE STUDY**

This is a multicentre, prospective, randomized, placebo-controlled, parallel group, double-blind, trial to compare the efficacy and safety of recMAGE-A3 + AS15 ASCI intramuscular injections with Placebo intramuscular injections.

The target was to enroll 273 patients to be randomly assigned to 2 treatment schedules in a 2:1 ratio, 2 patients randomized for recMAGE-A3 + AS15 ASCI versus 1 patient randomized for placebo, either directly after recovery from surgery, or after recovery from adjuvant chemotherapy. Ten European countries are participating with a total of 50 sites. Sites contributed 0-28 screened patients in the recruitment period of 40 months. Enrolment in this study was competitive.

As of 23 September 2014, the recruitment was put on hold (sites were still allowed until 3 February 2015 to randomize patients that signed the informed consent or were in the screening process).

[figure not shown]
As of Protocol Amendment 4.0, the recruitment will be stopped and the study will be unblinded (see for rationale Section 2.6.2).

For patients randomized to the placebo group, no further protocol visits will be performed except for the concluding visit and no further doses will be administered. The study will continue only with patients from the active treatment group who will decide to stay in the study. Patients receiving active treatment (patients not on placebo, and patients that have not already completed or interrupted their MAGE-A3 ASCI treatment) will be offered the option to continue the administration of the study treatment until the last dose is administered or until recurrence, whichever comes first, or until the patient or the investigator decides to stop the study treatment. The duration of the treatment period will not exceed 108 weeks for any patient, comprising the entire period of treatment administration and excluding the concluding visit (Visit 14), provided there are no postponements. The concluding visit will take place at least 30 days after the patient's

last dose of study product. Treatment will not be possible anymore after 30 November 2016. The 2,5-year active follow-up period planned in the initial study protocol has been cancelled. The total duration of the study will be 7 years. Data collection will be organised by Remote Data Entry on Electronic Case Report Forms (eCRF).

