## **6.4 Method of Blinding**

Initially the study was double-blind. As of Protocol Amendment 4.0, the recruitment will be stopped and the study will be unblinded.

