#### Visit 14: Concluding visit

This visit will take place at least 30 days after V13, approximately 120 weeks after first administration (V1) with a permitted deviation of up to 14 days, or in case of recurrence or early withdrawal.

The following procedures will be performed:

- Recording of concomitant medication
- Recording of (serious) adverse events and potential Immune-Mediated Diseases
- Routine physical examination including WHO performance status assessment
- Cross-sectional imaging or Magnetic Resonance Imaging (CT scan or MRI of chest, abdomen and pelvis)
- Pregnancy test

A pregnancy test will be repeated every 3 months for females of childbearing potential and should be performed at any time during the study for all women of childbearing potential if the investigator or patient suspects that pregnancy has occurred while the subject was being treated on protocol therapy.

- Blood sampling for safety

Note that as of Protocol Amendment 4.0, Smoking status and blood sampling for immunological examination (optional, if patient specifically consents to this), as mentioned in the original protocol, will not be performed anymore.

As of Protocol Amendment 4.0 the follow-up visits have been cancelled.

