### **7.3.3 Recurrence or progression**

All types of recurrence will be included i.e. local, regional and distant metastasis as well as second primary tumor of the upper urinary tract. In addition, all deaths occurring without prior documentation of tumor recurrence will be considered as an event. Any new primary cancer will not be considered as recurrence and should be reported as SAE.

All recurrences must be documented by radiological evidence or biopsy, as determined by the investigator.

[figure not shown]
Suspicion of relapse based on physical examination findings or laboratory signs must be confirmed by radiological examination and/or biopsy.

Equivocal findings on standard radiological imaging should be confirmed by repeated examinations or cytology/histology or other imaging techniques.

In the event of unequivocal, objective recurrence (at scheduled or unscheduled visit), the investigator will determine and record the recurrence, withdraw the patient from the study treatment

and perform all procedures as defined for Visit 14 before administration of chemotherapy to treat the recurrence. The investigator must inform the Sponsor as soon as possible.

The algorithm below summarizes how the date of recurrence should be determined.

Cxr, Chest X-Ray.

[figure not shown]
\* Date of imaging if equivocal, date of unplanned visit if symptoms present without imaging evidence.

\*\* CxR, CT scan/MRI, Bone scan, Biopsy of suspect lesion, etc.

\*\*\* Date of initial imaging (Day X) if equivocal, date of additional examinations (Day Z) if patient initially symptomatic without objective recurrence

[figure not shown]
**Scenario A:** As soon as a planned CT scan /MRI shows objective recurrence, the patient will be considered to have had a recurrence on the day of this planned imaging (Day X).

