### 10.3 Statistical Analyses

As of Protocol Amendment 4.0, statistical analyses will not be assessed as planned. All clinical data collected in the study will be analysed descriptively. Please see Section 2.6.2 for the rationale.

Patient characteristics, demographics and baseline measurements will be summarized in order to provide a characterization of the patient population. Descriptive statistics, e.g. mean, standard deviation, median, range, frequency distributions as appropriate will be presented for each randomization group: recMAGE-A3 + AS 15 ASCI versus the Placebo arm.

A yearly safety analysis will be performed until all patients have finished the treatment phase (Visit 14) which is 112 weeks after the last patient was randomized. The incidence and severity of all adverse events will be tabulated per treatment group. Treatment related toxicity > grade 2 will be descriptively described in both arms.

The description of the safety data will be performed, first globally then for each of the study arms. The safety analysis will be performed in all patients who are randomized and who received at least one Study Treatment Administration.

The efficacy analysis will be performed including all patients who are randomized and who received at least one Study Treatment Administration.

Disease free Survival (Section 3.3) will be estimated by means of the Kaplan Meier method and comparison between treatment groups will be done by means of the log-rank test.

A Cox proportional hazards model will be applied to correct for treatment effects and to assess the influence of prognostic and confounding factors such as T category, Neo-adjuvant Chemotherapy vs. Adjuvant Chemotherapy vs. no chemotherapy, N category, gender, centre, multifocality of bladder carcinoma (Y/N), age (continuous), presence of Carcinoma in Situ (CIS) and gene profile population.

The analyses of other outcome measurements will be analyzed in an exploratory way with methods appropriate for the type of the variable. Both the safety data and the efficacy data will be summarized by appropriate descriptive statistics.

For each patient entering, the reason for discontinuation (e.g. patient decision, urologists decision, lack of efficacy, adverse events) should be clarified. The description of the reason for discontinuation will be performed.

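### After Amendment 4.0 the late part of the active-arm DFS curve rests on unblinded recurrence calls in patients who chose to stay, with almost no placebo counterpart, and the plan does not separate these from blinded outcomes

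*Combined protocol and SAP*

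**What the plan says.** **Who decides.** Section 7.3.3: "All recurrences must be documented by radiological evidence or biopsy, as determined by the investigator". On unequivocal recurrence, "the investigator will determine and record the recurrence, withdraw the patient from the study treatment". Relapse is also the first criterion for permanent stopping in section 6.3.2.2. No central or blinded reader is named. Section 12.3 has the principal investigator, who represents the sponsor, confirm tumour responses. It does not mention recurrences or blinding.

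**What Amendment 4.0 changes.** Section 6.4: "As of Protocol Amendment 4.0, the recruitment will be stopped and the study will be unblinded". Section 4: "The study will continue only with patients from the active treatment group who will decide to stay in the study". Under the synopsis, active-arm patients still on treatment "will be offered the option to continue the administration of the study treatment" until the last dose or recurrence. Table 5 and section 7.3.2 give them CT or MRI at each of Visits 6 to 13. For placebo patients, "no further protocol visits will be performed except for the concluding visit and no further doses will be administered" (section 4). The concluding visit, Visit 14, also includes CT or MRI.

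**What is analysed.** Section 3.3 censors event-free patients at their last assessment. Sections 3.3, 3.4 and 10.3 say the endpoints will not be analysed as planned and that all clinical data will be described. Section 10.3 nevertheless keeps this text: "Disease free Survival (Section 3.3) will be estimated by means of the Kaplan Meier method", followed by a log-rank comparison of the arms. No section sets a cut at unblinding, a marker for calls made before or after it, or a sensitivity analysis.

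**The concern.** Up to unblinding, the two arms have the same scan schedule and the person deciding on recurrence does not know the arm. Afterwards both conditions fail, and they fail differently by arm. The continuing patients are all on active treatment, so the investigator knows the arm. They are also the ones who chose to go on, and a positive call ends the treatment they chose to keep.

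Kaplan-Meier copes with unequal follow-up if censoring is non-informative and events are ascertained alike in both arms. It does not correct for outcome assessment that differs by arm, or for who opted in. The same applies to disease-free specific survival (DFSS) and distant metastasis-free survival (DMFS), which use the same recurrence calls. At stake is how a reader of the final report should take the right-hand part of the by-arm curves.

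**Working it through.** **1. The plan's own figure.** The plan gives no number on this point. Its event target can be reproduced with Schoenfeld's formula, E = (z_α + z_β)² / [p(1−p)(ln HR)²], where p = 2/3 and alpha is one-sided 0.05. For HR 0.75 at 50% power, (1.645 + 0)² / (0.2222 × 0.0828) = 147.1, so 148 after rounding up, against 147 stated in section 10.1. The sample size is not in dispute; the same variance term is used in step 5.

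**2. Inputs for an illustration.**
- From the documents: 83 patients randomized when recruitment was put on hold; 2:1 allocation; 40 months of recruitment; median DFS 24 months on placebo; treatment to week 108; no treatment after 30 November 2016.
- Assumed, because the documents do not say: uniform accrual; exponential DFS with the same median in both arms (true HR 1); unblinding at month 41 or 46; 50% or 100% of on-treatment active patients staying; a placebo concluding visit one month after unblinding. The true number randomized may exceed 83, since sites could randomize until 3 February 2015.

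**3. Departures imposed on continuing active patients.** (a) None. (b) Every event is called one 12-week visit late. (c) 25% of events are never called. (d) Both (b) and (c). Each cell is 1,500 runs.

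**4. Results.** With data cut at unblinding there are 35.3 events (month 41) or 41.5 events (month 46), and the HR is 1.003 or 1.015. Without a cut:

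| Unblinding, opt-in | Post-unblinding events under (a): active / placebo | HR (a) | HR (b) | HR (c) | HR (d) |
|---|---|---|---|---|---|
| Month 41, 50% | 4.4 / 0.5 | 1.011 | 0.960 | 0.971 | 0.938 |
| Month 41, 100% | 7.7 / 0.4 | 1.005 | 0.961 | 0.955 | 0.913 |
| Month 46, 50% | 2.8 / 0.4 | 1.004 | 0.992 | 0.991 | 0.977 |
| Month 46, 100% | 4.8 / 0.4 | 0.995 | 0.958 | 0.977 | 0.935 |

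The share of active-arm events arising after unblinding runs from 2.8/30.9 = 9% to 7.7/31.4 = 25%.

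**5. Scale.** The standard error of ln HR is about 1/√(E × 2/9), which is 0.357 at 35.3 events and 0.329 at 41.5. The largest shift is ln(1.005/0.913) = 0.096, just over a quarter of one standard error. Simulation error on ln HR is about 0.34/√1500 = 0.009, so the departures from 1 in column (a) are mostly noise.

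**6. What the illustration overstates.** It delays or drops all events among continuing patients, deaths included, and it ignores the back-dating rules in section 7.3.3. It also imposes departures in one direction only.

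**The case against.** The strongest reply is that Amendment 4.0 has already taken the weight off this curve. The endpoints will not be analysed as planned, the data are to be described, and development of the product as a standalone treatment has stopped. This stands, and it limits how much the point matters. It does not remove the problem, because section 10.3 still describes DFS curves by arm.

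Four further points stand in part.
- **Placebo is not without unblinded assessment.** A reader might infer that only active-arm patients are assessed after unblinding. The documents do not support that, because each placebo patient has a concluding visit with CT or MRI. Only serial assessment is confined to the active arm.
- **Evidence constrains the call.** Radiology or biopsy is required, and section 12.1 allows reports to be requested for source verification. The plan does not say who reads the scans, only who determines recurrence. Judgement remains over whether imaging is objective, equivocal or negative.
- **An equivocal scan does not by itself delay an event.** Scenario B dates a confirmed recurrence back to the first equivocal scan. A delay needs a scan called negative, or a recurrence never confirmed.
- **Deaths from any cause count as DFS events** and are not open to this kind of judgement.

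**Conclusion.** The gap is real: following the plan as written mixes blinded outcomes in both arms with unblinded, opt-in outcomes in one, and nothing marks the difference. Closing it is a cheap improvement to a descriptive display. It does not repair a confirmatory analysis, since none remains.

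Two stronger readings should be resisted. One is that the curve is biased towards active treatment. Wanting to keep treatment could soften calls, but the amendment follows a negative phase III trial and the end of development, and nothing in the documents shows which way investigators would lean. The other is that the share of events after unblinding (9% to 25% here) measures bias. It measures exposure to possible bias. With unbiased calls the hazard ratio stays at about 1.00 to 1.01. It reaches about 0.91 to 0.99 only when late or missed calls are imposed.

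Even the largest shift is small against the imprecision: at 38 events the 95% interval around a hazard ratio of 1 is exp(±1.96 × 0.344), or 0.51 to 1.96. All these sizes rest on the assumed unblinding date, opt-in rate and accrual pattern.

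**What to change.** In sections 3.3 and 10.3, with matching wording for DFSS and DMFS in section 3.4:

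- Make the main by-arm display one that is cut at the unblinding date in both arms. Count events dated on or before it, and otherwise censor at the last assessment before it.
- Flag each recurrence by whether the deciding call was made before or after unblinding. An event-date cut alone is not enough: a scan that is equivocal before unblinding and confirmed after it is dated back under Scenario B, and Scenarios C and D likewise date a confirmed recurrence to the earlier equivocal examination. State how many events in the main display depend on such a call.
- Report later active-arm recurrences and deaths, and placebo concluding-visit findings, separately as open-label data. Keep the all-data curve as a supplement.

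The cost is some wording, one flag per recurrence, and a code-break date per patient, which the documents do not say is recorded. The main display loses a few late events in both arms, including deaths and placebo concluding-scan findings. They remain in the separate reports.

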**Scenario A**

[figure not shown]
**Scenario B:** If a planned imaging is equivocal, a confirmatory examination (imaging or biopsy) will be planned within 8 weeks after the first equivocal imaging. If this confirmatory examination shows an objective recurrence, the patient will be considered to have had a recurrence on the day of the first equivocal imaging (Day X). On the other hand, if the patient's condition does not allow for this confirmatory examination and another anti-cancer treatment is started, the patient will be considered to have had recurrence on the day of the first equivocal examination (Day X).

**Scenario B**

**Scenario C:** If a planned imaging does not show any objective recurrence but the patient is symptomatic, additional examinations will be conducted as clinically indicated (Chest X-Ray, CT scan/MRI, bone scan, biopsy, etc.). If objective recurrence is demonstrated, the date of this additional imaging or biopsy will be considered as the date of relapse (Day Z). However, if these additional examinations are equivocal or if symptoms persist without any explanation, confirmatory examination will be performed within 8 weeks as in scenario B. If recurrence is confirmed or if the patient requires immediate treatment with another anti-cancer therapy, the patient will be considered to have had recurrence on Day Z.

[figure not shown]
**Scenario C**

**Scenario D:** If a patient comes to an unplanned visit due to symptoms, additional examinations will be conducted as clinically indicated (Chest X-Ray, CT scan/MRI, bone scan, biopsy, etc.). If objective recurrence is demonstrated, the date of this additional imaging or biopsy will be considered as the date of relapse (Day Z).

If these additional examinations are equivocal, confirmatory examination will be performed within 8 weeks as in scenario B. If recurrence is confirmed or if the patient requires immediate treatment with another anti-cancer therapy, the patient will be considered to have had recurrence on Day Z. However, if these additional examinations are negative but symptoms persist without any explanation, and the patient requires immediate treatment with another anti-cancer therapy, the patient will be considered to have had recurrence on date of unplanned visit.

## Scenario D

In case of a bladder cancer recurrence a urine sample at the time of recurrence was collected and intended for analysis of MAGE A3 expression. In case a biopsy (resected tissue) of the recurrence was performed, we were interested in testing the recurrence for MAGE-A3 expression and in performing gene profiling research on the samples taken during biopsy.

The patient has signed a specific separate informed consent form to allow these tests. Instruction for sample handling and dispatch were given in the Laboratory Manual.

As of Protocol Amendment 4.0, no additional urine samples and/or biopsy tissues will be taken and collected for these tests.

## 7.4 Biological Sample Handling and Analysis

Table 7 summarizes all biological sample assays to be performed during this study.

As of Protocol Amendment 4.0 no more biological samples for protocol research purposes will be taken. This applies to every research topic (mandatory or optional) listed in this chapter, except for the sampling done for safety evaluation (hematology, renal function and hepatic function). By default, for each biological sample already collected in the scope of this study and not tested yet, testing will not be performed except if a scientific rationale remains relevant despite the premature termination of the study. In this case, testing will be done in compliance with the protocol and ICF signed by the patient. The immunological read-outs will not be performed anymore. Please see Section 2.6.2 for the rationale.

### 7.4.1. Treatment and storage of biological samples

See Laboratory manual.

**Table 7: Laboratory Assays**

Assay type	Test	Sample type	Laboratory	Timing
MAGE-A3 expression (mandatory at screening)*				
	MAGE-A3 expression testing	FFPE block 10mm  (or exceptionally 20-25 slides )	GSK Bio or contracted lab	During screening and in case of recurrence (in the latter case, after patient consent has been obtained)
Laboratory assays (mandatory)				
	Hematology White blood cell count Neutrophils Platelets Lymphocytes Hemoglobin			1. During screening (Visit S2), 2. Visit 5 3. Every year post-Visit 1 until concluding visit (i.e. at Visit 8 and 12), 4. At concluding visit (Visit 14).
	Renal function Creatinine	Blood (15ml)	Investigator laboratory	
	Hepatic function Serum bilirubin Aspartate transaminase (ASAT) Alanine transaminase (ALAT) Alkaline phosphatase			
Translational research (mandatory)				
Gene profiling				
	Gene profiling of primary tumor	FFPE tumor tissue	GSK Bio, Sponsor or contracted lab	After resection
Translational research (optional)				

MAGE-A3 expression testing	Urine (min 30 cc)	GSK Bio, Sponsor or contracted lab	During screening (S1) and in case of recurrence in urinary urothelium
Gene profiling of recurrent tumor b	FFPE tumor tissue	GSK Bio, Sponsor or contracted lab	In case of recurrence
Tumor antigen and MAGE A3 expression c	FFPE or Fresh tumor tissue	GSK Bio, Sponsor or contracted lab	
Gene profiling of primary or recurrent tumor c	Fresh tumor tissue	GSK Bio, Sponsor or contracted lab	
Demethylation c	Urine/blood / RNALater or FFPE tumor tissue	GSK Bio, Sponsor or contracted lab	
Tumor-related DNA Biomarkers c	RNALater or FFPE tumor tissue/Urine	GSK Bio, Sponsor or contracted lab	
Analysis of tumor environment	RNALater or FFPE tumor tissue/Urine	GSK Bio, Sponsor or contracted lab	

a) A total of 2 x 5 ml of blood will be used for immunological read-outs

b) Including MAGE-A3 expression testing

c) No additional samples are needed for this analysis

\*Note that as of Protocol Amendment 4.0 recruitment will be stopped and no more screening (and MAGE-A3 expression testing) will take place. During the treatment period, blood sampling and testing for safety monitoring will continue as initially foreseen during the treatment period. No more biological samples for immunological readouts or translational research will be collected. On the biological samples already collected, laboratory assays will only be performed if a scientific rationale remains relevant despite the premature termination of the study. The immunological read-outs will not be performed anymore. See Section 2.6.2 for the rationale.

Samples will not be labeled with information that directly identifies the patients but will be coded with a unique number for the sample.

It is also possible that future findings may make it desirable to use the samples acquired in this study for tests that are not related to the product or disease under study. Therefore, all patients will be invited to give their separate agreement (tick box in the Informed Consent form) to allow the sponsor or the company supplying the trial medication and its collaborating labs to perform such additional testing.

